### 5.4 Duration of Therapy

In the absence of treatment delays due to adverse event(s), treatment may continue until one of the following criteria applies:

- Disease progression with the caveat that patients that are clinically well may continue

on therapy following RECIST progression with new lesions or increase in target lesions if the increase in disease burden does not meet the definition of PD by immune response criteria [79] per [Section 11.2](#). (In this situation, patients do not have unequivocal progression until immune response criteria are met.)

- Intercurrent illness that prevents further administration of treatment
- Significant toxicity even after two reductions to lower dose levels, or no lower dose level exists (as described in [Section 5.1](#))
- Patient decides to withdraw from the study
- General or specific changes in the patient's condition render the patient unacceptable for further treatment in the judgment of the investigator

## **5.5 Duration of Follow Up**

Patients will be followed for toxicity for 120 days, until all toxicity resolves, or until they start another treatment, whichever is shortest. Patients removed from study for unacceptable adverse event(s) will be followed at least until resolution or stabilization of the adverse event.

## **5.6 Criteria for Removal from Study**

Patients will be removed from study when any of the criteria listed in Section 5.4 applies. The reason for study removal and the date the patient was removed must be documented in the Case Report Form.

# **6. DOSING DELAYS**

There are no dose reductions permitted for the ipilimumab and nivolumab study agents; dose delay and management tables are included below. Dose modifications that can be considered for rhIL-15 are described in Section 6.1.

Any unexpected grade 4 or grade 5 adverse event considered to be at least possibly related to study drug will cause the protocol to be halted and the study design and informed consent reevaluated with the sponsor.

## **6.1 Dose Delay Criteria**

For toxicities that are not defined as DLT, next drug doses can be delayed for up to +3 days to allow for toxicities to resolve. Patients who meet criteria to resume treatment, the dosing days of nivolumab and ipilimumab may be adjusted within a +3 day window, as long as consecutive nivolumab doses are given at least 12 days apart. Patients who do not meet the criteria to resume treatment will be managed as specified in the dose delay and adverse event management tables below.

**If study treatment is held for >42 days, the patient will go off study.**

While doses are being held, the patient will continue to progress through the treatment cycle. When the patient is able to resume treatment, restart drug administration as soon as possible based on the cycle schedule. Omit any missed doses.

### **rhIL-15 Dose Delays**

Patients should be monitored specifically for rhIL-15-associated toxicities that overlap with nivolumab and ipilimumab toxicity. These events include hypotension, hypoxia, rapid changes in peripheral blood lymphocytes, LFT elevation, and skin and organ infiltrates.

If a patient requires steroid treatment to manage toxicities, rhIL-15 should be held until the patient is tapered off steroids. IL-15 will be held for neutropenia grade 2 or higher (continuing other study drugs) if the patient is receiving benefit at the discretion of the PI in consultation with the medical monitor.

Neutropenia	Management/Next Dose for rhIL-15
≤ Grade 1	No change in dose
Grade 2 *	Hold until ≤ Grade 1. Resume at same dose level.
Grade 3 *	Hold* until < Grade 2.
Grade 4	Off protocol therapy

\* For neutropenia that does not improve to grade 1 within a 2-week time frame to resume re-treatment patients may be considered for dose-reduction of IL-15 or discontinuation at the discretion of the PI and in consultation with the medical monitor.

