## 5.2 Definition of Dose-Limiting Toxicity

Dose escalation will be based on DLTs observed during the first cycle of treatment.

**5.2.1** Grade  $\geq 3$  non-hematologic toxicity will be considered dose limiting, with the following exceptions:

- 5.2.1.1 Grade 3 fatigue lasting  $\leq 7$  days.
- 5.2.1.2 Grade 3 diarrhea will only be considered dose limiting if it is caused by colitis or, if after 72 hours, it is refractory to treatment. Grade 4 diarrhea will be dose limiting.
- 5.2.1.3 Grade 3 nausea and vomiting will only be considered dose limiting if after 72 hours it is refractory to maximal anti-emetic therapy and unable to be corrected to Grade  $\leq 2$  or baseline.
- 5.2.1.4 Grade 3 rise in creatinine, not corrected to Grade 1 or baseline after intravenous fluids within 24 hours, will be considered dose limiting. All Grade 4 rises in creatinine will be dose limiting.
- 5.2.1.5 Grade 3 electrolyte toxicities unable to be corrected to Grade 2 or baseline within 24 hours will be considered dose limiting.
- 5.2.1.6 Grade 3 liver function test (ALT, AST, alkaline phosphatase, total bilirubin) abnormalities in the absence of clinical signs of hepatic dysfunction (lethargy, confusion, anorexia, pruritus, tremor) that persist  $\leq 3$  days will not be considered dose-limiting.

**5.2.2** Grade 4 hematological toxicity

- 5.2.2.1 Neutropenia: Grade 4 neutropenia of any duration accompanied by fever or infection will be considered dose limiting. Grade 4 neutropenia for  $>5$  days without fever or infection will be considered dose limiting. Transient neutropenia ( $\leq 5$  days) without fever or infection will not be considered dose-limiting. Twice weekly blood draws will be needed (after onset of grade 4 neutropenia) to monitor duration of neutropenia for the first 2 cycles. On subsequent cycles (cycle 3 and beyond), weekly blood draws will be monitored after onset of grade 4 neutropenia.
- 5.2.2.2 Thrombocytopenia: Grade 4 thrombocytopenia will be considered dose limiting. Grade 3 thrombocytopenia associated with bleeding will be considered dose limiting.
- 5.2.2.3 Anemia: Grade 4 anemia will be considered dose limiting.

**5.2.3** Any neurotoxicity Grade  $\geq 2$  that is not reversible to a Grade  $\leq 1$  within 2 weeks will be considered dose limiting.

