**Note:** The optimal treatment regimen for immune-mediated myocarditis has not been established. Since this toxicity has caused patient deaths, an aggressive approach is recommended.

Recommended management: See Myocarditis Management Algorithm ([Appendix C](#))

Neutropenia	Management/Next Dose for Ipilimumab and Combination Nivolumab/ipilimumab
≤ Grade 1	No change in dose
Grade 2	Hold until ≤ Grade 1. Resume at same dose level.
Grade 3	Hold* until < Grade 2.
Grade 4	Off protocol therapy

\*Patients requiring a delay resulting in >2 missed doses should go off protocol therapy.

Thrombocytopenia	Management/Next Dose for Ipilimumab and Combination Nivolumab/Ipilimumab
≤ Grade 1	No change in dose
Grade 2	Hold until ≤ Grade 1. Resume at same dose level.
Grade 3	Hold* until < Grade 2.
Grade 4	Off protocol therapy

\*Patients requiring a delay of >2 weeks should go off protocol therapy.

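### The neutropenia instructions contradict each other at Grades 2 to 4, and a short Grade 4 event in cycle 1 could be counted as no DLT, a DLT or a replacement

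*Combined protocol and SAP*

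**What the plan says.** **Section 6.1, rhIL-15 Dose Delays.** The text states that "IL-15 will be held for neutropenia grade 2 or higher (continuing other study drugs) if the patient is receiving benefit". In full, the qualification is "if the patient is receiving benefit at the discretion of the PI in consultation with the medical monitor". The table directly beneath, which governs the next rhIL-15 dose, holds rhIL-15 at Grades 2 and 3 without any such condition. Its Grade 4 row reads "Off protocol therapy".

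**Section 6.1, Nivolumab and Ipilimumab Dose Delays.** The introduction limits the tables that follow to adverse events specific to nivolumab or ipilimumab. The neutropenia table, printed after the cardiac guidance, is headed "Management/Next Dose for Ipilimumab and Combination Nivolumab/ipilimumab". Grade 2 reads "Hold until ≤ Grade 1. Resume at same dose level". Grade 3 reads "Hold* until < Grade 2", with the footnote "Patients requiring a delay resulting in >2 missed doses should go off protocol therapy". Grade 4 is again off protocol therapy. No row mentions benefit or discretion or refers back to the rhIL-15 sentence.

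**DLT and MTD rules.** Section 5.2.2.1 says "Grade 4 neutropenia of any duration accompanied by fever or infection will be considered dose limiting". Grade 4 neutropenia of more than 5 days without fever or infection is also a DLT; 5 days or less without either is not. Section 5.2.3.1 makes any adverse event that requires permanent discontinuation of study drugs a DLT, and section 13.1 says the same of permanent discontinuation of one agent. Under section 5.1.2.1, repeated in 13.1, a patient without a DLT who does not finish the 42-day first cycle is not evaluable for the MTD and is replaced.

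**The concern.** The protocol itself anticipates this toxicity: section 2.1.4 reports transient Grade 3/4 neutropenia with rhIL-15. Blood counts are weekly in cycles 1 and 2, and the first nivolumab and ipilimumab doses fall on day 8, the last day of the first rhIL-15 course. A low count can therefore coincide with a dosing decision, and an investigator cannot then follow every instruction in section 6.1.

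Two things are at stake. The first is consistent handling: two patients with the same event may or may not have their checkpoint inhibitors held. The second matters more to the primary objective. Escalation rests on DLT counts in groups of 3 to 6, and the rules do not say how one foreseeable cycle-1 event is to be counted.

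**Working it through.** No sample-size or power figure is in dispute, so the check is mainly a comparison of texts.

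**Step 1. Grade by grade.**

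| Grade | rhIL-15 sentence | rhIL-15 table | Nivolumab/ipilimumab table |
|---|---|---|---|
| 2 | hold rhIL-15, continue the others, subject to conditions | hold rhIL-15 | hold |
| 3 | same | hold rhIL-15 | hold |
| 4 | same (the sentence has no upper grade) | off protocol therapy | off protocol therapy |

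The conditions can be read in two ways.

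- They limit continuation of the other drugs. The sentence then grants an exception that the nivolumab/ipilimumab table lacks.
- They limit the rhIL-15 hold. The sentence then contradicts the unconditional holds in the table beneath it.

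Neither reading reconciles the text. At Grade 4 the two tables agree with each other, and the sentence disagrees with both.

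**Step 2. Does attribution separate the rules?** It would if neutropenia could be assigned to one agent. Sections 7.1.1, 7.1.2 and 7.1.3 list decreased neutrophil count for ipilimumab, nivolumab and rhIL-15 alike, and section 6.1 gives no attribution rule.

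**Step 3. Counting a Grade 4 event of 5 days or less, without fever or infection, in cycle 1.**

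| Rule taken to govern | Result |
|---|---|
| 5.2.2.1 exception, and the patient is held to have finished the cycle | no DLT, evaluable |
| Grade 4 row read as permanent discontinuation, with 5.2.3.1 | DLT |
| 5.2.2.1 exception, but the patient leaves before finishing cycle 1 (5.1.2.1) | not evaluable, replaced |

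This ambiguity would remain even if the rhIL-15 sentence were deleted, because it arises from the Grade 4 rows. The febrile or infected case quoted from 5.2.2.1 is not in conflict: it is a DLT on any reading.

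**Step 4. Consequence in the 3+3.** The escalation table in section 13.1 follows from P = (1−p)³ + 3p(1−p)² × (1−p)³. At p = 0.30 this is 0.343 + 0.441 × 0.343 = 0.494. For p = 0.10 to 0.60 the formula gives 0.906, 0.709, 0.494, 0.309, 0.172 and 0.082, against the stated .91, .71, .49, .31, .17 and .08. The table is correct, but it presumes that every patient is unambiguously a DLT or not. Under section 5.1.2.1, reclassifying one patient turns 0/3 (escalate) into 1/3 (expand to 6), or 1/3 into 2/3 (stop escalating).

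**Step 5. Exposure, as an illustration.** Assume Grade 2 neutropenia from day 8. Cycle-1 doses are nivolumab on days 8, 22 and 36 and ipilimumab on day 8. The delay window is +3 days, so the day-8 dose can be given up to day 11 and the day-22 dose up to day 25. Missed doses are omitted.

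| Neutropenia lasts through | Drugs held: nivolumab, ipilimumab | Drugs continued |
|---|---|---|
| day 10 | 3/3, 1/1 | 3/3, 1/1 |
| day 11 to 14 | 2/3, 0/1 | 3/3, 1/1 |
| day 25 | 1/3, 0/1 | 3/3, 1/1 |
| day 42 | 0/3, 0/1 | 3/3, 1/1 |

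These differences need the continuing branch to be open in cycle 1. First restaging is at 6 weeks ± 1 week, that is day 42 ± 7, or days 35 to 49. Radiographic benefit therefore cannot be known on day 8 or day 22, and at the earliest is known one day before the day-36 dose. The cycle-1 contrast arises only if benefit, which is undefined, is judged clinically before restaging, or if the condition does not limit continuation. From cycle 2 the obstacle falls away.

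**The case against.** The strongest defence is that the nivolumab/ipilimumab table is the default and the rhIL-15 sentence is a case-by-case exception, guarded by benefit, PI discretion and medical monitor consultation. Handling would then turn on a deliberate decision. The stated scope of the nivolumab/ipilimumab tables and the placing of the sentence under the rhIL-15 heading point the same way.

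Part of this stands. A reader might infer that nivolumab and ipilimumab are simply continued through neutropenia; the conditions rule that out. A reader might also infer that day-8 dosing in cycle 1 must differ according to which instruction is followed; on the exception reading, a patient who has had only the rhIL-15 run-in would not normally qualify, and both instructions lead to a hold.

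The defence does not remove the conflict. Nothing marks the sentence as an exception to the later table, the conditions may attach to the rhIL-15 hold instead, and attribution is unworkable without a rule. It also cannot explain Grade 4, where the sentence contradicts the table beneath it, and it does not touch the DLT question.

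A further objection is that a 3+3 makes no comparison between cohorts: each level is judged on its own DLT count. That is right. It disposes of any claim that cohorts are not comparable, but not of the ambiguity about what enters the count.

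**Conclusion.** The concern holds as an internal inconsistency in a safety instruction, and it should be corrected. The conflict at Grades 2 and 3 (a conditional continuation against an unconditional hold) and at Grade 4 (the sentence against both tables) is plain from the text. So is the three-way classification of a short, uncomplicated Grade 4 event in cycle 1, provided that going off protocol therapy is taken as permanent discontinuation on at least one reasonable reading.

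In size, one such patient is enough to change an escalation decision. Checkpoint-inhibitor exposure may differ between readings, more clearly from cycle 2 and in cycle 1 only under the assumptions in the working. The documents give no neutropenia rate or duration for this regimen, so the number of patients affected cannot be computed. They support neither a certain loss of cycle-1 doses nor a finding that dose levels have been made incomparable.

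**What to change.** Replace the rhIL-15 sentence and the two neutropenia tables in section 6.1 with one grade-by-grade instruction covering rhIL-15, nivolumab and ipilimumab, and align the scope statement that introduces the nivolumab/ipilimumab tables. It should state:

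- for each grade, which agents are held, continued or stopped, including nivolumab given without ipilimumab, which the present table heading does not name;
- whether benefit matters, how and when it is judged, and which action it conditions;
- whether attribution matters and, if so, how neutropenia is attributed in the combination.

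Then reconcile that instruction with sections 5.1.2.1, 5.2.2.1, 5.2.3.1 and 13.1. State how a Grade 4 event that meets the 5.2.2.1 exception but leads to going off therapy counts for DLT and for MTD evaluability, and how omitted cycle-1 doses affect evaluability.

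Which clinical rule applies is for the sponsor's clinical team. The cost is a protocol amendment to wording. The sample size and the escalation probabilities in section 13.1 are unaffected.

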### **Nivolumab and Ipilimumab Dose Delays**

Below are dose delay and management tables for nivolumab and ipilimumab, indicating when study drug should be held or discontinued due to nivolumab or ipilimumab –specific adverse events.

ALL OTHER EVENTS	Management/Next Dose for Nivolumab and Combination Nivolumab/ipilimumab
≤ Grade 1	No change in dose. Continue treatment.
Grade 2	Hold until ≤ Grade 1 OR baseline (exceptions as noted below)
Grade 3	Off nivolumab/ipilimumab therapy. For immune-related adverse events, hold nivolumab and ipilimumab until ≤ Grade 1 OR baseline; resume at the same dose level (exceptions as noted below).
Grade 4	Off nivolumab and ipilimumab therapy (exceptions as noted below)

Recommended management: As clinically indicated

- Any adverse event, laboratory abnormality, or intercurrent illness which, in the judgment of the investigator, presents a substantial clinical risk to the subject with continued study drug dosing should discontinue nivolumab/ipilimumab treatment.
- Any grade 2 drug-related uveitis or eye pain or blurred vision that does not respond to topical therapy and does not improve to Grade 1 severity within the re-treatment period OR requires

systemic treatment should discontinue nivolumab/ipilimumab treatment.

- Any grade 3 or 4 drug-related laboratory abnormality or electrolyte abnormality, that can be managed independently from underlying organ pathology with electrolyte replacement, hormone replacement, insulin or that does not require treatment does not require discontinuation.
- Patients requiring > two dose delays for the same event should go off protocol therapy. Patients may be dose-delayed for evaluation and restarted depending on results.
- Please note that grading and for hypophysitis with symptoms of headache, visual or neurologic changes or radiologic evidence of pituitary enlargement and other CNS events such as aseptic meningitis or encephalitis should be considered grade 3 events.

Skin Rash and Oral Lesions	Management/Next Dose for Nivolumab and Combination Nivolumab/ipilimumab
≤ Grade 1	Continue therapy. No change in dose.*
Grade 2	Monitor weekly until 1≤ Grade. May initiate intermediate potency topical steroids (and treatment for pruritis if needed). Resume at same dose level.
Grade 3	Hold* until ≤ Grade 1. Resume at same level at investigator discretion.
Grade 4	Off nivolumab and ipilimumab treatment.

*Patients with purpuric or bullous lesions must be evaluated for vasculitis, Steven-Johnson syndrome, TEN, and autoimmune bullous disease including oral lesions of bullous pemphigus/pemphigoid. Pruritus may occur with or without skin rash and should be treated symptomatically if there is no associated liver or GI toxicity. Note skin rash typically occurs early and may be followed by additional events particularly during steroids tapering.
	
Recommended management: see Skin AE management algorithm ( Appendix C )	

Diarrhea/ Colitis	Management/Next Dose for Nivolumab and Combination Nivolumab/ipilimumab
≤ Grade 1	Continue therapy. No change in dose.
Grade 2	Hold until baseline. Treat symptomatically, and restart if improved to baseline or grade 1 at investigators discretion. No change in dose. If worsening or no improvement at 4 weeks or documented colitis by colonoscopy permanently discontinue and initiate steroid treatment.
Grade 3	Discontinue nivolumab/ipilimumab therapy. Obtain colonoscopy, and treat symptomatically
Grade 4	Discontinue nivolumab/ipilimumab therapy. 
 
Patients with grade 2 symptoms but normal colonoscopy and biopsies may be retreated after resolution.
 
Patients who require steroids should be taken off nivolumab/ipilimumab treatment.
 
Please evaluate pituitary function prior to starting steroids if possible without compromising acute care.
 
Evaluation for all patients for additional causes includes C. diff, acute and self-limited infectious and foodborne illness, ischemic bowel, diverticulitis, and IBD.
 

Recommended management: see GI AE management Algorithm ( Appendix C )	

GI: Nausea/Vomiting	Management/Next Dose for Nivolumab and Combination Nivolumab/ipilimumab
≤ Grade 1	Continue therapy. No change in dose.
Grade 2	Hold pending evaluation for gastritis duodenitis and other immune adverse events or other causes. Resume at same dose level after resolution to ≤ Grade 1.
Grade 3	Hold pending evaluation until ≤ Grade 1. Resume at same dose level. If symptoms do not resolve within 7 days, patients should discontinue nivolumab/ipilimumab treatment.
Grade 4	Off nivolumab/ipilimumab treatment.
Patients with grade 2 or 3 N-V should be evaluated for upper GI inflammation and other immune related events.	

Liver Function: AST, ALT, Bilirubin	Management/Next Dose for Nivolumab and Combination Nivolumab/ipilimumab
≤ Grade 1	Continue therapy. No change in dose.
Grade 2	Hold until grade 1 or baseline. Resume at same dose level.
Grade 3	Discontinue nivolumab or nivolumab/ipilimumab treatment and monitor with twice weekly LFTs until Grade ≤ 2. Initiate steroid therapy.
Grade 4	Off nivolumab and nivolumab/ipilimumab therapy.

 
Continued treatment of active immune mediated hepatitis may exacerbate ongoing inflammation. Holding drug to evaluate LFT changes and early treatment are recommended.
 
	
Recommended management: see Hepatic AE management algorithm ( Appendix C )	

Pancreatitis Amylase/Lipase	Management/Next Dose for Nivolumab and Combination Nivolumab/ipilimumab
≤ Grade 1	Continue treatment. No change in dose.
Grade 2	Continue at current dose level. More frequent monitoring of lipase and amylase. Patients who develop symptomatic pancreatitis should have nivolumab/ipilimumab held if applicable and steroid treatment initiated if clinically indicated.
Grade 3	Hold until ≤ Grade 2. Resume at same dose level if asymptomatic. Patients who develop symptomatic pancreatitis should be taken off nivolumab/ipilimumab treatment. 
 
Monitor lipase and amylase once or twice weekly.
 
Optional radiographic evaluation if there is new onset of symptomatic pancreatitis. Continue at the current dose level or interrupt per investigator's discretion.
 

Grade 4	Hold until ≤ Grade 2. Resume at same dose level if asymptomatic. Patients who develop symptomatic pancreatitis should be taken off

Pancreatitis Amylase/Lipase	Management/Next Dose for Nivolumab and Combination Nivolumab/Ipilimumab
	
nivolumab and ipilimumab treatment.
 
 
• Monitor lipase and amylase once or twice weekly.
 
• Optional radiographic evaluation if there is new onset of symptomatic pancreatitis or new onset of DM
 
 
Patients who develop symptomatic pancreatitis should be taken off treatment.

For treatment management of symptomatic pancreatitis, please follow the Hepatic Adverse Event Management Algorithm ( Appendix C )	

Renal	Management/Next Dose for Nivolumab and combination Nivolumab/Ipilimumab
≤ Grade 1	No change in dose.
Grade 2	Hold until ≤ Grade 1. Resume at same dose level.
Grade 3	Hold until ≤ Grade 1. Resume at same dose level.
Grade 4	Off treatment

Endocrine: Hypophysitis Adrenal Insufficiency	Management/Next Dose for Nivolumab and Combination Nivolumab/Ipilimumab
≤ Grade 1	Asymptomatic TSH elevation*. Patients must be evaluated, endocrine consult. May continue treatment at same dose level at investigator discretion.
Grade 2	Hold until patients are on a stable replacement hormone regimen and symptoms resolve. If treated with steroids, patients must be stable off steroids for two weeks. Resume at same dose level.
Grade 3	Hold until patients are on a stable replacement hormone regimen and symptoms resolve. If treated with steroids, patients must be stable off steroids for two weeks. Resume at same dose level.
Grade 4	Off nivolumab/Ipilimumab treatment.

\*Patients with thyroiditis may be retreated on replacement therapy. Patients must be evaluated to rule out pituitary disease prior to initiating thyroid replacement. Please evaluate pituitary function before beginning steroid therapy or replacement therapy of any kind.

Note all patients with symptomatic pituitary enlargement, exclusive of hormone deficiency, but including severe headache or enlarged pituitary on MRI should be considered grade 3 events. Isolated thyroid or testosterone deficiency may be treated as grade 2 if there are no other associated deficiencies and adrenal function is monitored.

Recommended management: See Endocrine Management Algorithm ([Appendix C](#))

Pneumonitis	Management/Next Dose for Nivolumab and Combination Nivolumab/Ipilimumab	Toxicity management
≤ Grade 1	
Hold dose pending evaluation and resolution to baseline including baseline pO2. Resume no change in dose after pulmonary and/or ID consultation excludes lymphocytic pneumonitis.
	
For Grade 1 (radiographic changes only):
 
 
- Monitor and closely follow up in 2-4 days for clinical symptoms, pulse oximetry (resting and exertion) and laboratory work-up and then as clinically indicated
 
- Consider pulmonary and infectious disease consult
 

Grade 2	
Hold dose pending evaluation. Resume no change in dose after pulmonary and/or ID consultation excludes ipilimumab and associated lymphocytic pneumonitis. Off nivolumab/Ipilimumab if steroids are required.
	
For Grade 2 (mild to moderate new symptoms)
 
 
- Monitor symptoms daily and consider hospitalization
 
- Promptly start systemic steroids (e.g. prednisone 1-2 mg/kg/day or IV equivalent)
 
- Reimaging as clinically indicated
 
- If no improvement within 3-5 days, additional workup should be considered and prompt treatment with IV methylprednisolone 2-4 mg/kg/day to be started
 
- If still no improvement within 3-5 days despite IV methylprednisolone at 2-4 mg/kg/day, promptly start immunosuppressive therapy such as TNF inhibitors (e.g. infliximab at 5 mg/kg every 2 weeks).
 
 
Caution: rule out sepsis and refer to infliximab label for general guidance before using infliximab

Grade 3	
Hold dose pending evaluation. Resume no change in dose after pulmonary and/or ID consultation excludes ipilimumab and associated lymphocytic pneumonitis. Off nivolumab/Ipilimumab if steroids are required.
	
For Grade 3 or 4 (severe or new symptoms, new/worsening hypoxia, life threatening):
 
 
- Promptly initiate empiric IV methylprednisolone 1-4 mg/kg/day or equivalent
 
- Obtain pulmonary and infectious disease consult
 
- Hospitalize the subject
 
- Supportive care (oxygen etc.)
 
- If no improvement within 3-5 days, additional workup should be considered and prompt treatment with additional immunosuppressive therapy such as TNF inhibitors (e.g. infliximab at 5 mg/kg every 2 weeks) to be started.
 
 
Caution: rule out sepsis and refer to infliximab label for general guidance before using infliximab

Pneumonitis	Management/Next Dose for Nivolumab and Combination Nivolumab/ipilimumab	Toxicity management
		
using infliximab
 
 
- Once improving, gradually taper steroids over <math>\geq 28</math> days and consider prophylactic antibiotics, antifungals and in particular, anti-PCP treatment (please refer to current NCCN guidelines for treatment of cancer-related infections)
 

Grade 4	Off nivolumab/ipilimumab treatment.	See above
All Grades	
Distinguishing inflammatory pneumonitis is often a diagnosis of exclusion for patients who do not respond to antibiotics and have no causal organism identified including influenza. Most patients with respiratory failure or hypoxia will be treated with steroids. Patients who require steroids should be taken off nivolumab treatment. Bronchoscopy may be required and analysis of lavage fluid for lymphocytic predominance may be helpful. Patients with new lung nodules should be evaluated for sarcoid like granuloma.
 
The investigator is requested to differentiate between non-infectious pneumonitis, and infectious pneumonitis (viral, bacterial, or fungal), aspiration pneumonitis, or other pneumonitis clearly not due to a potential hypersensitivity reaction to the study agent infusions; and provide the basis for his/her assessment that it is infectious or other, as appropriate. The investigator is requested to report with the most specific clinical terms to describe the condition, not simple “pneumonitis”.
	

Additional guidance can be found in the Pulmonary Adverse Event Management Algorithm ([Appendix C](#)). Consider recommending seasonal influenza killed vaccine for all patients.

Fatigue	Management/Next Dose for Nivolumab and Combination Nivolumab/ipilimumab
$\leq$ Grade 1	Continue therapy. No change in dose.
Grade 2	Continue therapy. No change in dose.
Grade 3	Hold until $\leq$ Grade 2. Resume at same dose level.
Grade 4	Off nivolumab/ipilimumab therapy.

Fatigue is the most common adverse event associated with immune checkpoint therapy. Grade 2 or greater fatigue should be evaluated for associated or underlying organ involvement including pituitary, thyroid, and hepatic, or muscle (CPK) inflammation.

Neurologic events	Management/Next Dose for Nivolumab and Combination Nivolumab/ipilimumab
$\leq$ Grade 1	Hold dose pending evaluation and observation. Resume with no change in dose when resolved to baseline.
Grade 2	Hold dose pending evaluation and observation. Hold until baseline. Off protocol treatment if steroids are required. Resume at same dose level

Neurologic events	Management/Next Dose for Nivolumab and Combination Nivolumab/ipilimumab
	for peripheral isolated n. VII (Bell's palsy).
Grade 3	Off nivolumab/ipilimumab treatment.
Grade 4	Off nivolumab/ipilimumab treatment.
Patients who require steroids should be taken off nivolumab/ipilimumab treatment.	
Patients with any CNS events including aseptic meningitis, encephalitis, symptomatic hypophysitis, or myopathy, peripheral demyelinating neuropathy, cranial neuropathy (other than peripheral n. VII), GB syndrome, myasthenia gravis should be off study.	
Recommended management: See Neurologic Adverse Event Management Algorithm (Appendix C)	

Infusion reaction	Management/Next Dose for Nivolumab and Combination Nivolumab/ipilimumab
≤ Grade 1	No change in dose.
Grade 2	Hold until ≤ Grade 1. Resume at same dose level.
Grade 3	Hold until ≤ Grade 1. Resume at same dose level with pre-medication at the discretion of the PI.
Grade 4	Off treatment
Patients with fever should be evaluated as clinically appropriate. Patients may experience isolated fever during infusion reactions or up to several days after infusion. Evaluation over the course of 1-2 weeks should be done for other autoimmune events that may present as fever.	
The following prophylactic premedications for future infusions: diphenhydramine 25-50 mg (or equivalent) and/or paracetamol 325 to 1000 mg (acetaminophen) at least 30 minutes before additional nivolumab/ipilimumab administrations.	

Fever	Management/Next Dose for Nivolumab and Combination Nivolumab/ipilimumab
≤ Grade 1	Continue therapy. Evaluate and continue at same dose level
Grade 2	Hold until ≤ Grade 1. Resume at same dose level.
Grade 3	Hold until ≤ Grade 1. Resume at same dose level.
Grade 4	Off nivolumab/ipilimumab therapy
Patients with fever should be evaluated as clinically appropriate. Patients may experience isolated fever during infusion reactions or up to several days after infusion. Evaluation over the course of 1-2 weeks should be done for other autoimmune events that may present as fever.	
See table above for Infusion Reactions .	

